6.10.2 Data Management

Participants will complete questionnaires online or on paper, depending on the licencing rules of the questionnaires AACQ-6 and ACLQ must be completed on paper) and the participant's preference. Paper questionnaires will be sent to NCTU (by post or email if returned to sites) where they will be transcribed into the eCRF. Online responses will be stored directly in the eCRF.

Positive tests for COVID-19 during trial participation will be recorded on the eCRF following a review of patient medical notes/discussion with participants by site staff. COVID-19 infection testing will only be carried out as part of local standard care testing where required, there are no trial specific requirements. All local guidelines will be followed with regards to COVID-19 safety measures.

Further information on data collection and management processes are provided in the PUFFIN Data Management Plan.

Data may be entered onto paper Case Report Forms (CRFs) prior to entry onto the database. Staff will receive training on data collection and use of the online system (see Section 6.10.2).

Data collection, data entry and queries raised by a member of the PUFFIN trial team will be conducted in line with NCTU and trial specific Data Management Standard Operating Procedure.

Identification logs and enrolment logs will be kept at the trial site in a locked cabinet within a secured room.

Participant identifiable data will be stored on a Participants Database for the purpose of contacting participants to collect trial data etc., sending questionnaires and reminders and for sending newsletters during the trial. All participant identifiable data will be stored securely, with access only granted to those members of the study team who require it.

Clinical trial team members will receive trial protocol training. All data will be handled in accordance with the Data Protection Act 2018 and GDPR 2018 and any subsequent revisions.

Data will be entered under the participants PID number onto the central database stored on the servers based at NCTU. Access to the database will be via unique, individually assigned (i.e. not generic) usernames and passwords, and only accessible to members of the PUFFIN trial team at NCTU, PUFFIN study teams at sites and external regulators if requested. The servers are protected by firewalls and are patched and maintained according to best practice. The physical location of the servers is protected physically and environmentally in accordance with University of East Anglia's General Information Security Policy 3 (GISP3: Physical and environmental security).

The eCRF and associated code will be developed by NCTU Data Management, in conjunction with the PUFFIN trial team. The eCRF software will provide a number of features to help maintain data quality, including; maintaining an audit trail, allowing custom validations on all data, allowing users to raise data query requests, and search facilities to identify validation failure / missing data.

After completion of the trial the eCRF will be retained for at least 25 years on the servers of NCTU for on-going analysis of secondary outcomes.

The identification and enrolment logs, linking participant identifiable data to the pseudoanonymised PID, will be held locally by the trial site. This will either be held in written form in a locked filing cabinet or electronically in password protected forms on hospital computers. After completion of the trial the identification and enrolment logs will be stored securely by the sites for 25 years unless otherwise advised by NCTU.

6.10.3 Non-Adherence and Non-Retention

The consent form will explain that if a participant wishes to withdraw from the study the data and samples acquired prior to that point will be retained. Reason for withdrawal will be recorded, if given, as will loss to follow up.

Non-adherence to trial medication will be assessed through capsule counts of unused returned drug supplies at each relevant study visit. We will consider 80% adherence as required for inclusion in the per protocol analysis.

Where patients are unable or unwilling to continue to undertake study measurements/activities, the decision as to whether the participant should continue with trial treatment and/or follow-up assessments will be at the discretion of the local PI and/or CI.

6.10.4 Statistical Methods 6.10.4.1 Outcomes Primary outcome

The primary outcome, change in ACQ -6 mean score six months post-randomisation, will be analysed using a general linear model adjusting for stratification variables.

Secondary outcomes

ACQ-7, AQLQ, EQ5D-5L, FEV₁, FEF₅₀, SNOT-22 at 12 weeks and 24 weeks post randomisation will be analysed using a general linear model adjusting for stratification variables.

Lung function data will be analysed using a repeated measures model.

Eosinophil count at 12 weeks and 24 weeks post randomisation will be analysed using a general linear model adjusting for stratification variables.

EPA and DHA, estimated from the FFQ, will be analysed using a general linear model adjusting for stratification variables.

The number of asthma attacks will be analysed using a Poisson regression model adjusting for stratification variables.

The assumptions of all the models will be checked using residual analysis and, if appropriate, alternative methods will be used.

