6.6.1.6 Six Week Assessment

The following assessments should be completed at home at 6 weeks post-randomisation: ACQ-6, PEF, adverse event questionnaire and concomitant medication questionnaire. Site staff will contact participants by phone/video call to assess adverse events if they have been flagged on the questionnaire.

Where these assessments are completed as part of standard care and within the time frame permitted by and requirements of this protocol, the results may be recorded for those required at the 6-week study time point.

Participants completing paper-based questionnaires will be provided with a freepost envelope to return them to the trials unit otherwise they will be completed electronically via REDCap.

This assessment may take place +/- 1 week of the scheduled date.

6.6.1.7 12 Week Study Visit

The following assessments should be completed 12 weeks post-randomisation: ACQ-6, PEF, PNIF, AQLQ, SNOT-22, spirometry, FeNO, RBC fatty acids and blood for eosinophils and safety monitoring and urine pregnancy test for WOCBP. Site staff will assess adverse events (including asthma attack frequency) and any changes to concomitant medication and/or medical history.

IMP adherence will be measured by a pill count completed by site staff/participant during the visit. This may be conducted at site where visits take place in person or participants will be asked to confirm the number of remaining capsules via phone/video call. If the participant has reduced their trial treatment dose due to adverse reaction(s) or intolerability this should be documented in the eCRF and a new dosing card administered. Participant should return the superseded dosing card either in person or via freepost envelope.

Participants completing paper-based questionnaires will be provided with a freepost envelope to return them to the trials unit otherwise they will be completed electronically via REDCap.

Where any of these assessments are completed as part of standard care and within the time frame permitted by and requirements of this protocol, the results may be recorded for those required at the 12 week study time point.

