6.6.3 Early Stopping of Follow-up

Sites must inform NCTU of all forms of early trial discontinuation via the eCRF. In instances where a participant has decided to withdraw consent, it is essential for the site to establish which aspects of the trial the participant is withdrawing consent from.

- If a participant chooses to discontinue their trial treatment, they should continue to be followed up as closely as possible to the follow-up schedule defined in the protocol, providing they are willing. They should be encouraged and facilitated not to leave the whole trial, even though they no longer take the trial treatment.
- If, however, the participant exercises the view that they no longer wish to provide data either through study visits or remotely via the registry, this view must be respected, and the participant withdrawn entirely from the trial. Data already collected will be kept and included in analyses according to the intention-to-treat principle for all participants who stop follow up early. Any samples provided by the participants, which have yet to be analysed will be destroyed and the registry will be updated so that no further data is provided to NCTU.

Where patients are unable or unwilling to continue to undertake study measurements/activities, the decision as to whether the participant should continue with trial treatment and/or follow-up assessments will be at the discretion of the local PI and/or CI.

Participants who stop trial follow-up early will not be replaced.

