6.10 Data Collection, Management and Analysis

6.10.1 Data Collection Methods

An on-line patient screening log will contain the details of the patient initials, date of contact and the route of identification for all potential participants who have received a patient information sheet (PIS). Following confirmation of consent, each participant will be given a unique trial Participant IDentification Number (PID). Data will be collected at the time-points indicated in the Schedule of Assessments (see section 6.6).

Data collection will vary according to the data variable in question.

1) ACQ is recognised by the American Thoracic Society and NICE and widely used in research (http://www.qoltech.co.uk/index.htm). The ACQ-7 has seven items: five questions about symptoms, one about reliever inhaler usage and a measure of airflow. The five symptom questions enquiring are 1) woken at night by symptoms, 2) wake in the mornings with symptoms, 3) limitation of daily activities, 4) shortness of breath and 5) wheeze. Patients are asked to recall how their asthma has been during the previous week and to respond using a 7-point scale (0 = no impairment, 6 = maximum impairment). Clinic staff score the FEV1% predicted on a 7-point scale. ACQ-7 score is the mean of the 7 questions and therefore between 0 (totally controlled) and 6 (severely uncontrolled). The ACQ-7 is validated using FEV1 and although sometimes PEF is used in its place, this is not recommended. The ACQ-6 (ACQ-7 without lung function assessment) is also validated and reflects the weekly impact of asthma on the individual. We have chosen the ACQ-6 (symptoms and beta agonist usage) as this does not require measurement of spirometry, which is considered an aerosol generating procedure, and there is high agreement between the different versions of the ACQ (37). It will be measured every 6 weeks.

2) Asthma Quality of Life Questionnaire.

Mini Asthma Quality of Life Questionnaire (mini-AQLQ) will be measured at baseline, 12 weeks and 24 weeks. It is a 15-item questionnaire as is a short version of the complete 32-item questionnaire. It comprises four domains (symptoms, environment, emotions, activities) and assess the previous 2-week period. Scores range from 0-6 (lower is worse). The mini-AQLQ score is calculated as the average of domain items(26). The minimum clinically important difference is 0.5.

3) Health related quality of life.

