6.10.4.3 Additional Analyses

Adjusted analyses will be undertaken for the outcomes by adjusting for the baseline value of the respective outcome measure. The primary analysis will be that adjusting for baseline.

Additional adjusted analyses may be undertaken for factors known to be associated with the outcome as decided by the TMG prior to analysis.

A sensitivity analysis will be undertaken based on those with a RBC EPA+DHA enrichment of 2.7-fold.

Further exploratory analyses maybe undertaken, but these will be detailed in the SAP prior to analysis.

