6.10.4.5 Missing Data

The pattern of missing data will be assessed and if appropriate, multiple imputation will be used to account for missing data under the assumption that the data are missing at random. If the data are not considered missing at random then a sensitivity analysis of the results will be undertaken by considering appropriate scenarios, such as the worst-case scenario or pattern-mixture models.

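### The week-24 ACQ-6 analysis is valid, but it uses interim ACQ-6 only if imputation is later judged appropriate, and the MNAR sensitivity analysis hangs on a judgement the data cannot settle

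*Protocol*

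**What the plan says.** **Primary model.** Protocol section 6.10.4.1 specifies a single-timepoint model: "change in ACQ -6 mean score six months post-randomisation, will be analysed using a general linear model", with adjustment for the stratification factors. Section 6.10.4.3 adds baseline: "The primary analysis will be that adjusting for baseline". Read together, the primary analysis is an analysis of covariance of ACQ-6 at week 24.

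**Data collected.** Section 6.10.1, item 1, says of ACQ-6: "It will be measured every 6 weeks". The schedule in section 6.6 and the visit descriptions in 6.6.1.6 to 6.6.1.9 place it at weeks 6, 12, 18 and 24; for week 6, for example, "The following assessments should be completed at home at 6 weeks post-randomisation: ACQ-6, PEF". The structured summary (1.3) lists six-weekly ACQ-6 among the secondary outcomes.

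**Expected loss.** Section 6.7 assumes 20% withdrawal, SD 0.67, a difference of 0.5, 90% power and 98 randomised.

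**Missing data.** Section 6.10.4.5 provides for multiple imputation under MAR where this is thought appropriate. Then: "If the data are not considered missing at random then a sensitivity analysis of the results will be undertaken", with worst-case or pattern-mixture approaches as examples.

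**Early leavers.** Section 6.6.3: "Data already collected will be kept and included in analyses according to the intention-to-treat principle". Section 6.10.4.4 defines the intention-to-treat set as all randomised individuals.

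**Lung function.** Section 6.10.4.1 lists FEV1 and FEF50 under a general linear model at weeks 12 and 24, and then says: "Lung function data will be analysed using a repeated measures model".

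**The concern.** Two stated rules are at issue.

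First, a week-24 general linear model fitted to observed data uses nobody without a week-24 value. At the planned 20% withdrawal that is about 20 of 98 participants (0.20 × 98 = 19.6). Many of them may have ACQ-6 at week 6, 12 or 18, which says something about where they were heading. Whether it is used depends on a later decision about imputation.

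Second, the MNAR analysis has a trigger that cannot work. Comparing leavers with stayers on baseline and interim values can show that dropout depends on what was observed. It cannot show whether, given those values, dropout also depends on the unseen week-24 score, and that is the whole difference between MAR and MNAR. So the decision to test robustness rests on opinion, formed after the missing-data pattern has been inspected. A SAP that follows this rule inherits the problem.

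At stake are a little precision, protection against dropout that depends on interim control differently by arm, and a guaranteed test of how far the result leans on MAR.

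**Working it through.** **1. The plan's own figure.** Inputs from section 6.7: difference 0.5, SD 0.67, alpha 0.05 (taken as two-sided; not stated), power 0.90, withdrawal 20%.
- Normal approximation: n = 2 × (1.960 + 1.282)² × (0.67/0.5)² = 37.7, so 38 per arm.
- t-based: 38.7, so 39 per arm. 39/0.80 = 48.75, so 49 per arm and **98 in total**. The stated figure is reproduced.

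**2. Power from observed week-24 values.** 49 × 0.80 = 39.2 per arm. Power = Φ[0.5/(0.67 × √(2/39.2)) − 1.960] = Φ(3.304 − 1.960) = 0.911 (0.904 by t).

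**3. Gain from the interim visits.** Visit correlation and dropout timing are not in the protocol. Assumed: correlation ρ of 0.6 to 0.8, exchangeable or AR(1). Everything is conditional on baseline, because the primary model is baseline-adjusted.

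If all dropout follows week 18, there is a closed form. Let R² be the share of week-24 variance explained by weeks 6 to 18, given baseline. Then effective n = 49 / [(1 − R²)/0.80 + R²].
- Exchangeable: the partial correlation between visits is r = (ρ − ρ²)/(1 − ρ²), and R² = 3r²/(1 + 2r). For ρ = 0.8, r = 0.444 and R² = 0.314, giving 41.8. For ρ = 0.6, r = 0.375 and R² = 0.241, giving 41.2.
- AR(1): only week 18 matters, and R² = (ρ − ρ⁷)² / [(1 − ρ⁸)(1 − ρ⁶)]. For ρ = 0.8, R² = 0.567, giving 44.2. For ρ = 0.6, R² = 0.349, giving 42.1.

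The other patterns use the same generalised least squares information, summed over dropout groups:

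| Timing of the 20% dropout | Effective n per arm | Gain over 39.2 | Power |
|---|---|---|---|
| All before week 6 | 39.2 | 0 | 0.911 |
| 5% before each of weeks 6, 12, 18, 24 | 40.3–41.4 | 1.1–2.2 | 0.918–0.925 |
| One third after each of weeks 6, 12, 18 | 40.7–42.1 | 1.5–2.9 | 0.920–0.928 |
| All after week 18 | 41.2–44.2 | 2.0–5.0 | 0.923–0.939 |

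Conditioning on baseline matters: a correlation of 0.8 falls to 0.44. A calculation that ignores baseline reaches about 45 per arm, which overstates the gain.

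**4. Bias when dropout depends on interim ACQ-6.** Large-sample simulations, SD 0.67, true difference 0.50. The rows with 20% loss in each arm use exchangeable correlation 0.5 or 0.7. All mechanisms are assumed.

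| Dropout mechanism | Observed week-24 estimate | Attenuation | With interim visits |
|---|---|---|---|
| Same dependence and same 20% loss in both arms | 0.50 | none | 0.50 |
| Follows last ACQ-6, loss 17–25% by arm | 0.486, 0.475, 0.469 | 3%, 5%, 6% | 0.499–0.504 |
| Tied to poor control on placebo only, 20% per arm | 0.46 | 8% | 0.50 |
| Opposite dependence in the two arms, 20% per arm | 0.44 | 11–12% | 0.50–0.51 |

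**5. What the interim visits cannot do.** A repeated measures model also assumes MAR. If the 20% missing in the active arm alone were worse by δ than MAR predicts, the estimate would move by 0.20 × δ. As an illustration, δ = 0.5 moves it by 0.10, a fifth of the target difference. Only a sensitivity analysis that departs from MAR examines this.

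**The case against.** The chosen model is a standard, legitimate one. Multiple imputation under MAR that included interim ACQ-6 would recover essentially what a repeated measures model recovers, and the choice of imputation variables is properly left to the SAP, which is not at hand. Sections 6.4.7 and 6.6.3 keep participants who stop treatment in follow-up, which limits missing week-24 values. The precision gain is small and the bias depends on mechanisms the protocol does not describe. All of this stands, and it makes the change of model an improvement rather than a correction of an error.

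Stronger readings are tempting, and the documents do not support them:
- *That the primary analysis breaches intention-to-treat or section 6.6.3.* Section 6.6.3 promises that collected data will be used in analyses, not that every interim value enters the primary model. Six-weekly ACQ-6 is itself a secondary outcome, and imputation is one way to include all randomised participants.
- *That the primary estimate is biased.* It is not, if dropout has the same rate and the same dependence in both arms.
- *That missing data are ignored or the sample size is wrong.* Section 6.10.4.5 addresses missing data, and 98 reproduces.
- *That the lung-function wording shows the primary model to be inconsistent.* Those are secondary outcomes, and the repeated measures sentence may mean the six-weekly PEF only.

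What the objection does not meet is the MNAR trigger. It is a rule stated in the protocol, and no data can settle it.

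**Conclusion.** The point holds in a limited form. The baseline-adjusted week-24 model is valid, but the protocol does not commit to using the interim ACQ-6, and it makes the MNAR sensitivity analysis depend on a judgement that observed data cannot inform. The second part carries most of the weight.

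The size is modest. With evenly spread dropout the gain is about 1 to 2 points of power; it is about 3 at most, if all dropout follows week 18, and nil if it all precedes week 6. The 3 to 12% attenuation applies only where dropout differs between arms in its rate or its dependence on interim ACQ-6. These ranges rest on assumed correlations, timing and mechanisms; 49 per arm, 20% loss, SD 0.67 and the 0.5 difference come from the protocol. The required sample size does not change.

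**What to change.** Before unblinding, amend sections 6.10.4.1 and 6.10.4.5 and carry the changes into the SAP.

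1. Make the primary analysis a baseline-adjusted repeated measures model on ACQ-6 at weeks 6, 12, 18 and 24, with unstructured covariance, visit, visit-by-arm and visit-by-baseline terms, and the stratification factors. The week-24 contrast is the primary estimate. Alternatively, keep the week-24 model and commit to multiple imputation that includes the interim ACQ-6.
2. Always run a prespecified delta-based or tipping-point MNAR sensitivity analysis, whatever is believed about the missingness.
3. Separately, state which single model applies to FEV1 and FEF50, and whether the lung-function sentence means PEF only or includes them.

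The cost is protocol and SAP wording and a little programming. No new data are needed, and the endpoint, the primary contrast and the sample size stay as they are.

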5.1.1 Explanation for choice of comparators

N-3 PUFA will be compared with matched placebo as this is the most robust way to determine the efficacy and adverse effects of n-3 PUFA. All patients involved in the trial will continue to receive usual care (defined in section 6.4.5).

Treatment allocation is double-blind to reduce potential bias in reporting of the primary outcome and patient reported secondary outcomes.

5.2 **Objectives**

The primary research hypothesis is that participants treated with n-3 PUFA will have greater improvement in asthma control as measured by the ACQ-6 test at 24 weeks post-randomisation versus participants treated with placebo.

The secondary research hypotheses are that participants treated with n-3 PUFA will:

- Have better asthma control as measured by the ACQ-7 test.
- Have better asthma related quality of life as measured by the asthma quality of life questionnaire (AQLQ).
- Have better health related quality of life measured by the euro-qol (5L-EQ-5D).
- Have better airway calibre as measured by peak expiratory flow (PEF), forced expiratory volume in 1 second (FEV₁) and forced expiratory flow at 50% of vital capacity (FEF₅₀).
- Have better peak nasal inspiratory flow (PNIF).
- Show n-3 PUFA is well tolerated with an acceptable safety profile.

Mechanistic research hypotheses are that the participants treated with n-3 PUFA will:

- Have reduced type 2 airway inflammation as assessed by FeNO, blood eosinophils and sputum eosinophils (subgroup).
- Have reduced urinary leukotriene E4 (uLTE4) and urinary prostaglandin D2 (PGD₂) concentration.
- Have improved Red Blood Cell (RBC) fatty acid concentration.
- Have increased sputum SPMs (subgroup).

Exploratory research hypotheses are:

- that participants treated with n-3 PUFA will have a reduced frequency of asthma attacks.
- those with higher baseline uLTE4 will have a greater response to n-3 PUFA.
- the greatest benefits will be evident in those with low baseline RBC omega-3 index.
- changes in RBC fatty acid concentration will relate to the clinical and mechanistic responses.

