5.3 Trial Design

The study is a Phase III double blind, parallel group, 1:1 randomised, placebo controlled, multi-centre, clinical superiority trial of oral n-3 PUFA versus placebo in 98 participants with N-ERD and uncontrolled asthma. Outcomes will be assessed during a treatment period of 24 weeks. The primary endpoint is change in ACQ-6 mean score measured between baseline and 24 weeks post-randomisation of n-3

PUFA versus placebo. A subgroup of 52 participants (26 per group) will be recruited into the sputum sub-study. Randomisation will be performed centrally according to a computer-generated randomisation code by secure automated e-mail from NCTU to site pharmacies only. Stratification factors are: recruiting site and inclusion into sputum subgroup.

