• A urine sample will be collected at baseline and after 24 weeks of therapy. It will be analysed for LTE4 and PGD2 by radioimmunoassay and corrected for urinary creatinine.

Adherence

 Venous blood will be collected at baseline, 12 weeks and 24 weeks for assessment of red blood cell fatty acid concentration. In the situation that venous blood is not available, red blood cell fatty acid concentration will be obtained from a finger prick blood sample, which will be collected using a dried blood spot sample card and mailed to the Norwich Research Park Biorepository. • Food frequency questionnaire (FFQ) will be completed at baseline and 24 weeks using the validated European Prospective Investigation of Cancer (EPIC) FFQ(33). The FFQ will be analysed using the online McCance and Widdowson's composition of foods integrated dataset, in order to establish habitual dietary intake, and in particular EPA and DHA.

Specialised pro-resolving mediators (SPM)

 Induced or spontaneous sputum (subgroup) will be collected at baseline and 24 weeks for SPM. Sputum samples will be acidified, applied to solid-phase extraction cartridges and the eluted SPM will be analysed by liquid chromatography-tandem mass spectrometry as described by Barden et al (34).

Asthma attacks and safety:

- Asthma attacks will be defined as those resulting in death, hospitalisation, A&E attendance, out-of-hours medical contact, or a course or boost in oral corticosteroids (prednisolone) of at least 3 days for asthma.
- Adverse events will be recorded at each study visit following randomisation.
- Full blood count, renal and liver function tests, and coagulation for those receiving warfarin will be measured in local laboratories at baseline, 12 weeks and 24 weeks.

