12) Urine pregnancy tests (WOCBP only) will be measured at baseline and 12 weeks.

13) Food frequency questionnaire (FFQ).

This will be performed at baseline, and 24 weeks using the validated European Prospective Investigation of Cancer (EPIC) FFQ(33), with the FFQ recognised as a robust methodology to capture habitual diet and is particularly suited to quantify foods not consumed on a daily basis, such as fish (main dietary source of EPA and DHA). The FFQ will be analysed using the online McCance and Widdowson's composition of foods integrated dataset, in order to establish habitual dietary intake; in particular, EPA and DHA.

14) Asthma attacks.

Asthma attacks will be defined as those resulting in death, hospitalisation, A&E attendance, out-ofhours medical contact, or a course or boost in oral corticosteroids (prednisolone) for asthma. The number of asthma attacks over the duration of the study will be captured.

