6.10.4.2 Statistical Analysis Plan (SAP)

A full SAP will be produced prior to the analysis of any data. Both the TSC and DMC will be given the opportunity to comment on the SAP prior to it being signed-off by the CI and lead statistician.

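### Two protocol sections define an asthma attack differently, so the count depends on which is followed; the Poisson analysis of that count should also name follow-up time and allow for clustering

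*Protocol*

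**What the plan says.** Protocol section 6.5.2, under asthma attacks and safety, lists what counts as an attack: death, hospitalisation, emergency department attendance, out-of-hours contact, or "a course or boost in oral corticosteroids (prednisolone) of at least 3 days for asthma". Section 6.10.1, item 14, repeats the list but ends it with "a course or boost in oral corticosteroids (prednisolone) for asthma", and adds: "The number of asthma attacks over the duration of the study will be captured".

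On analysis, section 6.10.4.1 says: "The number of asthma attacks will be analysed using a Poisson regression model adjusting for stratification variables". It names no exposure term. It closes with a clause covering every model: "The assumptions of all the models will be checked using residual analysis and, if appropriate, alternative methods will be used". Section 6.10.4.2 adds: "A full SAP will be produced prior to the analysis of any data".

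On standing, section 5.2 lists as an exploratory hypothesis "that participants treated with n-3 PUFA will have a reduced frequency of asthma attacks". Section 6.5.2 places attacks among the secondary outcomes, and section 6.10.4.1 analyses them under that heading.

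On follow-up, section 5.3 says: "Outcomes will be assessed during a treatment period of 24 weeks". The last visit has a window of 4 weeks either side (section 6.6.1.9). Data from participants who stop follow-up early stay in the intention-to-treat analysis (section 6.6.3). The sample size in section 6.7 assumes 20% withdrawal.

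**The concern.** Both attack definitions stand in operative sections, and each is worded as the definition. One sits with the outcomes and the other with the data collection instructions. Staff who work from section 6.10.1 would record a two-day steroid course as an attack, whereas an analyst who works from section 6.5.2 would exclude it. If the eCRF holds only a number of attacks, the stricter definition cannot be applied afterwards, whatever the SAP says. At stake are the count itself and its comparability across sites.

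The analysis sentence raises a lesser matter. A Poisson model of a number, without person-time, compares counts rather than rates, although the hypothesis is about frequency and observation time will differ between participants. The Poisson model also takes the variance to equal the mean. If some patients are prone to repeated attacks, the variance is larger and the standard error is too small.

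**Working it through.** **1. The definitions side by side**

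| Criterion | Section 6.5.2 | Section 6.10.1, item 14 |
|---|---|---|
| Death, hospitalisation, A&E, out-of-hours contact | counts | counts |
| Oral steroid course of 3 days or more | counts | counts |
| Oral steroid course of 1 or 2 days, no other criterion met | does not count | counts |

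Only the last row differs. Its effect on the count equals the number of such courses, for which the documents give neither a figure nor a basis for one.

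**2. Variation in follow-up**

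- Final visit between 24 − 4 = 20 and 24 + 4 = 28 weeks; 28/20 = 1.40 between the two extremes.
- A participant who leaves at week 12 has 12/24 = half the exposure of a 24-week completer.

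**3. Effect on a Poisson test**

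The protocol states no attack rate, dispersion or power for attacks, so there is no figure of its own to reproduce.

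Inputs from the protocol: 49 per arm, 24 weeks, 20% withdrawal, significance level 0.05 (taken as two-sided).

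Assumed inputs: 0.5, 1 or 2 attacks per year; gamma-Poisson counts with variance = mean + k × mean², k from 0 to 2; dropout times uniform over the 24 weeks.

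Method: 40,000 simulated trials per case with no true effect and a Wald test of the log ratio of arm totals, with standard error √(1/a + 1/b), where a and b are the totals. The simulation uses neither stratification terms nor the visit window.

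Type I error with 20% dropout in both arms, without / with a log person-time offset:

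| Attacks per year | k = 0 | k = 0.5 | k = 1 | k = 2 |
|---|---|---|---|---|
| 0.5 | 4.3% / 4.1% | 5.3% / 5.0% | 6.8% / 6.0% | 9.0% / 8.4% |
| 1 | 5.0% / 4.7% | 7.6% / 7.0% | 9.7% / 9.4% | 14.5% / 14.5% |
| 2 | 5.5% / 4.9% | 10.6% / 10.0% | 16.0% / 15.1% | 23.6% / 23.1% |

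The mean rate ratio is about 1.00 throughout. Clustering drives the inflation, and an offset does not remove it.

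Check by formula at 1 attack per year:

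- Mean count = (24/52) × (1 − 0.20/2) = 0.415.
- Variance/mean φ = 1 + k × 0.415 = 1.21, 1.42 and 1.83 for k = 0.5, 1 and 2.
- Type I error = 2 × (1 − Φ(1.96/√φ)), about 7.5%, 9.9% and 14.7%, in line with the simulation.

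**4. Unequal dropout, assumed 30% v 10%, k = 0**

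Expected exposure ratio = (1 − 0.30/2)/(1 − 0.10/2) = 0.85/0.95 = 0.895.

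| Attacks per year | No offset: rate ratio, type I error | Offset: rate ratio, type I error |
|---|---|---|
| 0.5 | 0.889, 4.8% | 0.990, 4.0% |
| 1 | 0.892, 6.3% | 0.997, 4.5% |
| 2 | 0.893, 8.3% | 0.999, 4.7% |

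**The case against.** The conflict of definitions can be played down but not removed. The protocol's trial diagram section refers readers to section 6.5 for outcomes, which favours the 3-day text. The trial is double-blind, so whichever definition is used should apply alike to both arms, and no directional bias is shown. Changes in concomitant medication are recorded (section 6.4.5), so course length might be recoverable, although the protocol does not say that durations are captured. These points lessen the harm; two operative texts still disagree.

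The objection to the analysis part is stronger. An offset is commonly left to the SAP, which is promised and not shown. The model-check clause allows another method if the Poisson assumptions fail. Participants who stop treatment are meant to stay in follow-up (sections 6.4.7 and 6.6.3), and hospital admissions are sought even after withdrawal (section 6.6.5), so the 20% withdrawal figure is not a rate of lost attack data. The visit window is the same in both arms. Adjustment for prior attacks is arguably provided already, since section 6.6.1.4 collects 12-month attack frequency and section 6.10.4.3 adjusts outcomes for their baseline value. All of this stands, which is why the analysis part is a suggestion.

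A reader might go further and infer three things that the documents do not support:

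- That the protocol treats early leavers as fully observed. It neither states nor excludes an exposure term.
- That the error rate depends on which definition is followed. The definition decides which events count, and there is only one analysis text.
- That the error rate reaches 26%. The formula gives that at φ = 3, but at one attack per year this needs k = (3 − 1)/0.415 = 4.8, for which the documents give no basis.

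**Conclusion.** The contradiction between sections 6.5.2 and 6.10.1 is established from the text alone and should be reconciled. Its size is unknown. Which definition is right is the sponsor's decision and is not judged here.

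The analysis sentence is not an error, but it can be improved cheaply. At an assumed one attack per year, k of 0.5 to 2 and equal dropout, plain Poisson has a type I error of about 7% to 15%. Across 0.5 to 2 attacks per year the range is about 5% to 24%, and without clustering the error is close to nominal. The missing offset causes little bias when dropout is equal and moves the null rate ratio to about 0.89 at an assumed 30% v 10%. All of these figures rest on assumed attack rates, dispersion and dropout patterns.

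Attacks do not enter the sample size, so the 98 participants, the 90% power and the primary outcome are unaffected.

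**What to change.** 1. Put one definition, chosen by the sponsor, in both section 6.5.2 and section 6.10.1, item 14. Record the length of each oral steroid course in the eCRF so that the definition can be applied. Cost: protocol wording and, if not already present, one eCRF field. This is best done while data are still being collected.

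2. In section 6.10.4.1 or the SAP, pre-specify negative binomial regression for attacks, or Poisson with robust variance (also the fallback if the negative binomial model does not converge), with log follow-up time as offset. State how follow-up time is measured for participants who stop early. If the baseline adjustment in section 6.10.4.3 is meant to cover attacks, say that the 12-month attack history is the covariate.

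Cost: wording, and wider intervals where attacks cluster. Under the assumptions above the widening is about √φ: 1.10, 1.19 and 1.35 times at k of 0.5, 1 and 2. Plain Poisson would understate that uncertainty. Without clustering the price is small.
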